### 5.2 Treatment Regimen

1. Patients seen at Stanford University Digestive Health Center who meet study inclusion criteria will be screened for enrollment. Those patients with diagnosed functional dyspepsia, idiopathic or diabetic gastroparesis will be considered eligible. Those who do not meet any exclusionary criteria will then be actively enrolled in the study. Study subjects who sign informed consent to participate in the study will have a baseline history and physical exam, and baseline laboratory tests to be completed after baseline endoscopy and at the time of first (pre-treatment) gastric emptying testing.
2. Patients will complete the following forms at the time of study enrollment:
  - GCSI-DD (Gastroparesis Cardinal Symptom Index Daily Diary)
  - GI PROMIS belly pain questionnaire.
  - PROMIS Global Health Short Form questionnaire.
  - PROMIS Pain Interference Short Form 8a questionnaire.
  - Short Form SF-12 questionnaire.
  - Compass 31 Survey
3. After successful baseline upper endoscopy and subsequent gastric emptying testing with associated baseline HRV, blood, urine, saliva, and stool tests, patients will start active VNS treatment. The first gammaCore device therapy will be done in the office to ensure proper use, tolerability, and address any questions or concerns patients may bring up. The dosing of therapy will be personalized for each patient at this first session (by asking subject to increase dose until they experience a tug on the ipsilateral side of their mouth). This dose will then be maintained for the duration of the study. Posteriorly, 90-120 minutes after the first stimulation, a repeat blood collection will take place (two vials for Human 63-plex Luminex assay and banking) to assess the acute effect of the VNS treatment on inflammatory markers.

4. Total treatment duration will be 4 weeks. GammaCore administration will occur twice daily, in the morning and evening. Each treatment will entail a 2-minute application to the R and L cervical vagus nerve, each side separated by 3-5 minutes, for a total of 4 applications daily (total of 8 minutes).
5. Patients will receive weekly calls to assess compliance, tolerability, and reminders for their symptoms questionnaires.

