6. Patients will present to endoscopy for their post-treatment upper endoscopy 4 weeks after initiation of therapy. No later than 3 days after endoscopy, patients will present to clinic at which time post-treatment gastric emptying testing, HRV testing, and laboratory tests (blood and stool) will be obtained, and the aforementioned forms will again be completed.
7. Patients will be seen in clinic again at 4 weeks after discontinuation of therapy, and undergo a repeat medical history and physical exam. At this time gastric emptying testing, HRV testing, and laboratory tests (blood and stool) will again be obtained; and the aforementioned forms will again be completed to assess whether any change in symptoms and disease severity has occurred off therapy.

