	(baseline) Visit 1 Enrollment	≤ 8 wk prior (baseline) Visit 2 Endoscopy	Day 0 (start VNS) Visit 3 Clinic	Day 28 ( Visit 4 Endoscopy VNS 4 Weeks	Day 31 End VNS) Visit 5 Clinic	Day 51 (Washout) Visit 6 Clinic
Inclusion criteria met, no exclusion criteria met	X					
Informed consent	X					
Medical History	X		X		X	X
Physical Exam	X		X		X	X
Medication Rev	X		X		X	X
Blood collection: CBC, BMP, LFT, A1C, β-HCG, ESR, CRP, 63-plex Luminex ,and Heparin vials for FACS analysis			X	X		X
			X	X		X
			X	X		X
			X	X		X
			X	X		X
			X	X		X
Forms GI PROMIS pain PROMIS Health PROMIS Pain SF_12_Health COMPASS 31	X		X		X	X
	X		X		X	X
	X		X		X	X
	X		X		X	X
	X		X		X	X
	X		X		X	X
	X		X		X	X
GCSI-DD HRV-app	← 8 weeks. (2 weeks before VNS, 4 weeks of VNS, 2 weeks after VNS) →					
EGD		X		X		
HRV / EKG			X		X	X
Gastric Emptying			X		X	X
Stool collection			X		X	X
Saliva collection			X		X	

Adverse reactions	X	X	X	X	X	X

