## **7. Statistical Analysis Plan**

The mean baseline GCSI aggregate score will be compared with the mean aggregate score at the end of each treatment week, and in the 4 subsequent weeks after therapy discontinuation. Paired Student T-tests will be done comparing baseline with all other subsequent time points. Gastric emptying times will be plotted before treatment, at the end of treatment, and four weeks after end of treatment and compared by ANOVA. Similarly, differences among the three subgroups of patients will be determined at baseline and after treatment.

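### The schedule table stops the GCSI diary two weeks after VNS and dates Visit 6 at Day 51, so it cannot supply the four-week off-therapy comparisons planned in section 7

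*Combined protocol and SAP*

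**What the plan says.** **Diary.** In the schedule of assessments (Study Assessment and Monitoring), the GCSI-DD shares a row with the HRV app. That row spans eight weeks, split as "2 weeks before VNS, 4 weeks of VNS, 2 weeks after VNS". Item 2 of the same section instead has the diary filled in every day for as long as the study runs. Section 7 compares mean baseline GCSI with each treatment week "and in the 4 subsequent weeks after therapy discontinuation", and adds: "Paired Student T-tests will be done comparing baseline with all other subsequent time points".

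**Visit 6.** The table column reads "Day 51 (Washout) Visit 6". Section 5.2 item 7 places this clinic visit four weeks after therapy stops. Section 3.4 gives a four-week follow-up period. Sections 3.1 and 5.4 place the last visit and study completion at 8 weeks. Section 7 takes gastric emptying before treatment, "at the end of treatment, and four weeks after end of treatment and compared by ANOVA".

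**End of VNS.** Section 5.2 item 4 states: "Total treatment duration will be 4 weeks". The table starts VNS on Day 0 and has endoscopy on Day 28. The next column reads "Day 31 End VNS) Visit 5 Clinic", in a header that is split across two columns in the text available. Section 5.2 item 6 explains the later clinic day: "No later than 3 days after endoscopy".

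**Gastric emptying.** Item 1 of Study Assessment and Monitoring lists the test only at baseline and after the four weeks of therapy. Section 5.2 item 7, the table and section 7 all include an off-therapy test as well.

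**The concern.** The table is the only day-by-day schedule in the document, so staff are likely to work from it. Nothing says whether the table or the text prevails where they differ.

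The off-therapy comparisons are planned for both measures named as primary in section 3.3, and section 5.2 item 7 gives their purpose: to see whether symptoms and severity change once VNS stops. Under the table, the second half of that period has no daily symptom record, and unrecorded diary days cannot be recovered later. The gastric emptying result would exist, but a measurement taken about three weeks after therapy would be reported as a four-week one.

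The conflict is easy to miss because two different spans are both called 8 weeks. The diary's 8 weeks begin two weeks before VNS. The 8 weeks in sections 3.1 and 5.4 match four weeks on therapy plus four weeks off.

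**Working it through.** This is calendar arithmetic.

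**Inputs.** VNS starts on Day 0 (table) and lasts 4 weeks (section 5.2). The diary runs 2 + 4 + 2 weeks and Visit 6 is on Day 51 (table). The off-therapy period analysed is 4 weeks, or 28 days (section 7). VNS ends on Day 28 if the 4 weeks are counted from Day 0. Day 31 is carried as an alternative because of the split header.

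**Reproducing the table's diary span.** 2 + 4 + 2 = 8 weeks, which agrees with the table. The row is internally consistent, so a misread digit does not explain it. The span that section 7 needs, with the same two-week lead-in, is 2 + 4 + 4 = 10 weeks.

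**Reproducing Day 51.** Four weeks after the end of VNS is end day + 28. Eight weeks from Day 0 is 8 × 7 = Day 56. Shifting the day count by one either way gives Day 55 to 57 for a Day 28 end, and Day 58 to 60 for a Day 31 end. None of these is Day 51.

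| Quantity | VNS ends Day 28 | VNS ends Day 31 |
|---|---|---|
| Last diary day under the table (end + 14) | 42 | 45 |
| Last day of the four off-therapy weeks (end + 28) | 56 | 59 |
| Off-therapy diary days collected | 14 of 28 | 14 of 28 |
| Visit 6 minus end of VNS | 51 − 28 = 23 days (23/7 = 3.3 weeks) | 51 − 31 = 20 days (20/7 = 2.9 weeks) |
| Shortfall against four weeks | 56 − 51 = 5 days | 59 − 51 = 8 days |

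**Diary days by off-therapy week under the table.** 7 + 7 + 0 + 0 = 14 on either reading, so 14/28 = 50% are missing. Sections 5.2 items 2 and 7 together repeat the GCSI-DD form at the last visit. That adds at most one entry and does not give a weekly mean for week 3 or week 4.

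**Effect on the planned tests.** Section 7 does not say whether the off-therapy weeks are tested one by one or pooled. If they are tested one by one (an assumption), there are 4 + 4 = 8 weekly comparisons with baseline, and the table supplies diary data for 4 + 2 = 6. If they are pooled, the off-therapy mean covers only the first two of the four weeks.

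**Interaction of the two conflicts.** With VNS ending on Day 28, a diary kept daily but stopped at a Day 51 visit would give 23 of 28 days. Extending the diary alone therefore does not fully close the gap if participation ends at Visit 6 as dated.

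**The case against.** The strongest reply is that little depends on this. Section 4.2 defines the primary comparison as before against after VNS, and section 3.3 attaches no off-therapy time point to either primary endpoint. This is a single-arm pilot, and the off-therapy data are a look at durability. Off-therapy GCSI weeks 1 and 2 are still collected, and gastric emptying is still measured off therapy. Nothing in the documents shows that 23 days rather than 28 would change the emptying result. All of this stands. It makes the Visit 6 part a matter of labelling or a visit window, and leaves the diary gap as the more substantial part.

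A second reply is that the text, if followed, would supply the data. That is true, and the point is conditional on the trial being run by the table.

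A third is that the table was damaged in reading from PDF. The header is split, the diary row carries two items, and the forms and blood blocks do not line up with their labels. However, the diary wording and the Day 51 entry are intact, and both conflicts hold on either reading of the header.

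A reader might also infer that different sites would collect different data. The documents do not support that: sections 4.5 and 5.2 describe recruitment at one centre. The risk is that one team follows one version or the other.

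**Conclusion.** The point holds. The schedule table contradicts section 7 and the text on off-therapy follow-up. Under the table, 14 of 28 off-therapy diary days are not collected, and the only off-therapy gastric emptying test falls 5 days short of its stated time. This assumes daily diary entries, as item 2 of Study Assessment and Monitoring states, and VNS ending on Day 28, which fits the four-week duration and the clinic visit within three days of endoscopy.

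Two stronger conclusions are tempting but not supported:

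- An 8-day shortfall follows only if the split header is read as VNS ending on Day 31.
- The main efficacy comparison is not compromised, and the off-therapy gastric emptying result is mistimed rather than missing.

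The omission of the off-therapy test from item 1 of Study Assessment and Monitoring is a further inconsistency on the same point. This should be fixed because it affects planned analyses of both primary measures, but it does not invalidate the trial's main result.

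**What to change.** Reconcile sections 3.1, 3.4, 5.2 (items 6 and 7), 5.4 and 7 with items 1 and 2 of Study Assessment and Monitoring and with the schedule table. Specifically:

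- **Diary.** Either extend the GCSI-DD row to cover all four off-therapy weeks that section 7 analyses, or cut section 7 to the weeks collected. Because the HRV app shares the row, state whether it is extended too.
- **Visit 6.** Either make the table day agree with the four-week time point in section 7 and state a visit window, or relabel the section 7 time point to match the day scheduled.
- **End of VNS.** Show the last VNS day unambiguously in the table header, so that the off-therapy weeks have one starting point.
- **Off-therapy GCSI.** State in section 7 whether it is four weekly means or one pooled mean.
- **Gastric emptying.** Bring item 1 of Study Assessment and Monitoring into line with the other sections on whether there is an off-therapy test.

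The cost is protocol and SAP wording, at most two more weeks of a diary patients already keep (and of the HRV app, if that is extended), and a Visit 6 move of about 5 days or a relabel. No visit or procedure is added.

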### **5.3 *Implementation of Study Device***

Patients will be instructed in the application of the gammaCore device in clinic, and will receive printed materials to guide them in the proper use and implementation of the device.

#### **5.4    *Subject Compliance Monitoring***

Compliance will be assessed by weekly phone communications, during clinic visits at 4 weeks after initiation of therapy, and at study completion (8 weeks), by VNS device dosimeter reading.

#### **5.5    *Prior and Concomitant Therapy***

Participants will be allowed to continue steady doses of medications they are on for gastroparesis for 4 weeks prior to study enrollment. No new scheduled medications for gastroparesis can be initiated during the study period and they must remain on stable doses of any pre-existing medications being used for gastroparesis. The following as-needed rescue medications for symptom control will be allowed for use on a PRN basis during the study: ondansetron, promethazine, diphenhydramine, and Tylenol, toradol. Patients on daily use of narcotic pain medications within the preceding 4 weeks of screening will be excluded from the study and patients will be prohibited from taking opioid medications during the study period.

### **6        Safety and Adverse Events**

#### **6.1    *Risks***

There is a low reported incidence of adverse side effects with the use of transdermal VNS using gammaCore. There have been no reported incidences of cardiac arrest, respiratory depression, or other serious adverse events. In an IDE, prospective, multi-centered pilot study, no adverse events were reported during or after stimulation. There were no significant changes in electrocardiogram, heart rate or systolic or diastolic blood pressure (Engel et al Poster). Reported side effects are mild and include hoarseness, shortness of breath, change in voice, & skin irritation.

#### **6.2    *Recording of Adverse Events***

The principal investigator (PI) is responsible for monitoring the conduct of the study and the safety of the study subjects. The participants will be closely monitored by the PI for the development of any adverse events. If adverse events occur (whether expected or unexpected), the PI will evaluate the severity of the adverse event and will initiate immediate corrective measures. The PI will determine if any adverse event is attributed to the research study. All serious and/or unexpected adverse events will be reported to the IRB and appropriate federal agencies in a timely fashion. In particular, the investigator of an IDE such as this must notify in a written IDE safety report of any adverse experience associated with the use of the device that is both serious and unexpected. This notification must be made as soon as possible and no later than 15 calendar days after initial receipt of the information.

The PI will submit a yearly written progress report to the IRB for review. This report will also be sent to the FDA for review (see data collection section). This report will delineate the number of subjects entered into the study (in the past year and total), any

adverse events that have occurred in the past year, and the reason for any subject dropout/withdrawal from the study.

### **6.3 *Reporting of Adverse Events***

Within 60 days of the anniversary date that the IDE goes into effect (an IDE goes into effect 30 days after FDA receives it), a brief report of the progress of the investigation must be submitted to the FDA. This must include: 1) a brief summary of the status of each patient enrolled in the protocol; 2) the total number of subjects you plan to treat under the protocol; the number entered into treatment to date, and the number who dropped out of the study for any reason; 3) a description of the general investigational plan for the coming year.

## **7. Statistical Analysis Plan**

The mean baseline GCSI aggregate score will be compared with the mean aggregate score at the end of each treatment week, and in the 4 subsequent weeks after therapy discontinuation. Paired Student T-tests will be done comparing baseline with all other subsequent time points. Gastric emptying times will be plotted before treatment, at the end of treatment, and four weeks after end of treatment and compared by ANOVA. Similarly, differences among the three subgroups of patients will be determined at baseline and after treatment.

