## **3 Study Design**

### **3.1 General Design**

This is a prospective interventional pilot study assessing the safety and tolerability, as well as efficacy of the use of VNS in patients with idiopathic and functional gastroparesis. We will also include patients with functional dyspepsia, which have almost identical clinical symptomatology and are believed to share similar underlying inflammation and dysautonomia. We plan to recruit a total of 45 patients, 15 patients of each subgroup, for 4 weeks of therapy with VNS. Patients will undergo baseline measures of symptoms, gastric emptying testing, vagal tone, and inflammation. After enrollment, patients will undergo two upper endoscopies (pre and post therapy). Pt will be seen in clinic for recruitment, day 0, for follow-up at 4 weeks, and again at 8 weeks, for a total of six visits including their appointed endoscopy days.

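### Separate paired t-tests on exposure-worded GCSI weeks let patients who leave drop out of the later tests, so the week-4 effect may describe mainly those who continued

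*Combined protocol and SAP*

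**What the plan says.** Section 3.3 makes the GCSI the first primary outcome. Section 7 has its baseline mean "compared with the mean aggregate score at the end of each treatment week, and in the 4 subsequent weeks after therapy discontinuation", and gives the method: "Paired Student T-tests will be done comparing baseline with all other subsequent time points". It names no analysis population and no rule for missing scores.

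The documents describe time in two ways.

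- **By exposure.** Besides section 7, item 7 of section 5.2 places the last visit by the end of therapy: "Patients will be seen in clinic again at 4 weeks after discontinuation of therapy".
- **By study time.** Item 6 of section 5.2 schedules the "post-treatment upper endoscopy 4 weeks after initiation of therapy". Section 3.1 has patients seen "for follow-up at 4 weeks, and again at 8 weeks". Section 5.4 checks compliance "during clinic visits at 4 weeks after initiation of therapy, and at study completion (8 weeks". The visit table uses Days 0, 28, 31 and 51.

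The assessment list before the table has the GCSI diary completed every day for the length of the study. The table itself limits it to "2 weeks before VNS, 4 weeks of VNS, 2 weeks after VNS".

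Section 4.6 requires withdrawal for withdrawn consent or a serious adverse effect. It is silent on a patient who stops the device and stays in the study.

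**The concern.** A paired t-test needs a baseline and a later value from the same patient. Run separately at each time point, the tests use whoever is available that week. A patient who withdraws after week 2 counts in weeks 1 and 2 and then disappears. The sequence of weekly results therefore mixes change within patients with change in who is being measured.

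The exposure wording adds a second way out. An analyst could decide that weeks without the device are not treatment weeks and leave them out of the week-4 mean, even though the patient is still filling in the diary. Nothing in section 7 prevents this, and nothing requires it.

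This matters more here than in a controlled trial. Section 3.1 describes no control arm, so the pre/post contrast is the whole of the efficacy evidence. If patients who do not benefit are the ones who leave, the week-4 mean moves in the favourable direction and no comparison group would show it.

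**Working it through.** **1. What can be reproduced.** Section 4.2 gives 45 patients (3 × 15) and a GCSI reduction of at least 1 as the target. It gives no SD, no withdrawal rate and no early-stopping rate. Neither the sample size nor the loss of patients can therefore be derived from the documents. The point does not depend on the sample size.

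**2. Number of tests.** Four treatment weeks plus four later weeks gives up to 4 + 4 = 8 comparisons with baseline, each on its own set of available pairs.

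**3. Size of a possible overstatement.** Inputs:

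- continuers improve by 1.0 (assumed, set equal to the section 4.2 target);
- a proportion d leaves the week-4 test (assumed 10%, 20%, 30%);
- leavers improve by s (assumed 0 or 0.5).

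All-treated mean improvement = (1 − d) × 1.0 + d × s. A continuers-only test reports 1.0, so the overstatement is d × (1.0 − s).

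| d | s = 0 | s = 0.5 | Continuers only |
|---|---|---|---|
| 10% | 0.9 × 1.0 + 0 = 0.90 | 0.9 + 0.05 = 0.95 | 1.0 |
| 20% | 0.8 × 1.0 + 0 = 0.80 | 0.8 + 0.10 = 0.90 | 1.0 |
| 30% | 0.7 × 1.0 + 0 = 0.70 | 0.7 + 0.15 = 0.85 | 1.0 |

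The overstatement runs from 0.05 to 0.30 of a point over this grid. It is zero if leavers improve as much as continuers (s = 1.0). At d = 20%, 0.20 × 45 = 9 patients leave and 36 remain; in a subgroup, 3 of 15 leave and 12 remain.

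**4. Timing, taken separately.** These gaps affect every patient, whether or not anyone stops early.

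- Four weeks after Day 28 is 28 + 28 = Day 56, which is also week 8. Four weeks after Day 31 is 31 + 28 = Day 59. The table's Day 51 is 51 − 28 = 23 days after Day 28 and 51 − 31 = 20 days after Day 31.
- Section 7 analyses four GCSI weeks after therapy. The table collects the diary for two.

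**The case against.** A reader might go further and infer that section 7 and section 5.2 count weeks and the last visit from each patient's own stopping day. On that reading, a patient who stops on Day 10 is dropped from the week-4 test as the plan is written, and has a last visit on Day 10 + 28 = 38. The documents do not support this.

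- No passage refers to an individual or actual stopping day. Sections 3.4 and 5.2 fix therapy at four weeks for everyone, so discontinuation reads naturally as the planned end.
- Sections 3.1 and 5.4 and the visit table use fixed study time.
- The assessment list has the diary daily throughout, so a patient who stops on Day 10 but stays in the study can still supply weeks 2 to 4 and attend the end-of-treatment visits.
- The own-stop reading does not fit the visit table. Two diary weeks after a Day 10 stop end on Day 10 + 14 = 24, so four post-discontinuation weeks could not be filled.

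Those objections stand, and they limit the wording issue to something the plan permits.

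Two further objections also stand in part. Patients who stop for the mild effects listed in section 6.1, such as hoarseness or skin irritation, may have responded as well as anyone, in which case there is no bias. And in a 45-patient pilot a mixed model is no cure for withdrawals driven by responses that were never recorded.

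None of this touches the remaining problem. Under either reading of discontinuation, separate paired tests lose patients without a later score, and section 7 does not say how they are handled.

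**Conclusion.** The point holds in limited form. The stated method for the primary GCSI endpoint restricts each test to available pairs, so the week-4 result may describe a selected group and the weekly results may not be comparable. That much follows from the method once anyone has a missing later score. Moving early stoppers out of the treatment-week means is allowed by the wording but not prescribed.

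Upward bias is conditional on poorer response among those who leave. On the assumed grid it is 0.05 to 0.30 of a GCSI point against a target of 1. The documents give no rate with which to narrow this range. The change is worth making before the data are analysed, because it replaces a weak stated method with a better one at little cost.

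**What to change.** In section 7:

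- Define GCSI weeks from the first stimulation (Day 0) for all treated patients, whatever their later device use.
- State that the diary and visit data already planned are kept, and still collected, after the device is stopped.
- Make the primary GCSI result the week-4 change from a mixed model for repeated measures on the weekly means, in all treated patients. A patient with only some weeks then still contributes.
- Report two sensitivity analyses: patients still using the device, identified from the dosimeter reading in section 5.4; and a less favourable assumption for withdrawals, for example no change from baseline.

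Separately, reconcile the timing of the last visit (four weeks after discontinuation or week 8, against Day 51) and the length of the diary after therapy (two weeks in the visit table, four in section 7).

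**Cost.** The GCSI changes are wording in section 7 and add no assessments or patients. The estimate may be less favourable. The model assumes that missing scores are missing at random, which is why the withdrawal sensitivity analysis is needed.

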### **3.3 *Study Endpoints***

#### ***I. Primary Study Endpoints***

- 1.1 The primary outcome measure will be the effect of VNS on gastroparesis cardinal symptoms as measured by the gastroparesis cardinal symptom index (GCSI) questionnaire.
- 1.2 The second primary outcome measure will be the effect of VNS on gastric emptying time as measured by the gastric emptying spirulina breath test.

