#### ***4.2 Sample size justification***

- Total of 45 patients; 15 with functional dyspepsia, 15 with diabetic gastroparesis, and 15 with idiopathic gastroparesis.
- Primary comparison: Gastric emptying half time score and GCSI, pre and post VNS
- Error protection: Type I = 0.05 two-sided and Type II = 0.10 (80% power). To detect a clinically significant change of >30% in gastric emptying time, and a reduction in  $\geq 1$  GCSI aggregate.

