## **Study Assessment and Monitoring**

- 1. Spirulina Gastric Emptying Breath Test** (Viramontes et al 2001): Gastric emptying times will be measured at baseline and after 4-week therapy. As part of standard of care procedures, diabetic patients will have their blood sugar measured prior to this test. They will need to have a blood sugar level of less than 275 mg/dl, as this high level will results in artificially delayed emptying. Patients will be asked to reschedule if this is the case.
- 2. GCSI-DD[3]:** Gastroparesis-specific symptom severity scale. Obtained at baseline (1 week prior to randomization) and daily throughout the duration of the study.
- 3. GI PROMIS[2]:** publically available patient related outcome (PRO) measure that covers 8 symptom domains (Abdominal pain, Gas/Bloating, Diarrhea, Constipation, Bowel Incontinence, Reflux, Nausea and Vomiting, Disruptive Swallowing) that can be used together or individually to assess GI symptoms in clinical practice and research. Symptoms are assessed via 7-day recall. The questionnaire will be filled out one week prior to starting therapy and at each follow up visit.
- 4. PROMIS Global Health**
- 5. PROMIS Pain Interference**
- 6. Compass 31 Survey**
- 7. Human 63-plex Luminex assay:** The Human Immune Monitoring Center (HIMC) at the Stanford Institute for Immunity, Transplantation and Infection has a standardized immunoassay for the detection of 63 human serum cytokines and chemokines using a Luminex assay.
- 8. Flow Cytometry:** additional blood samples will be processed for storage, or for same-day in vitro re-stimulation assays in [name] research Laboratory at Stanford SOM.

**9. Dysbiosis:** stool samples will be frozen for storage until all subjects are enrolled. Subsequent metabolomics and 16S rRNA sequencing experiments will be done with collaborators of [name] at Stanford SOM.

**10. Upper GI Endoscopy:** All patients will receive standard of care and standard precautions for GI endoscopy as per Stanford Outpatient Endoscopy guidelines. Patients will undergo a baseline endoscopy, and again after VNS treatment to assess the impact of therapy on the target organ, i.e. the stomach. During the procedure, detailed endoscopic assessment of the mucosa will take place, including tissue biopsies that will be collected and processed in [name] at Stanford SOM.

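### One two-sided 0.05 is stated for two primary measures, but section 7 gives no success rule: the overall error is up to 9.75% if either measure suffices, and the rules that would hold 5% are not in the plan

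*Combined protocol and SAP*

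**What the plan says.** Section 3.3 names GCSI as the primary outcome and then adds "The second primary outcome measure will be the effect of VNS on gastric emptying time". It gives neither a time point. Section 4.2 gives the comparison as "Primary comparison: Gastric emptying half time score and GCSI, pre and post VNS" and the error rates as "Error protection: Type I = 0.05 two-sided and Type II = 0.10 (80% power" (the bracket closes there). The target effects follow: "To detect a clinically significant change of >30% in gastric emptying time, and a reduction in" GCSI of at least 1.

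Three places bear on what the post-VNS assessment is:

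- Study Assessment and Monitoring, item 1: "Gastric emptying times will be measured at baseline and after 4-week therapy".
- Section 5.2, item 6, describes the clinic visit after the 4-week endoscopy, "at which time post-treatment gastric emptying testing, HRV testing, and laboratory tests (blood and stool) will be obtained". The questionnaires, which include the GCSI daily diary, are repeated then.
- Section 5.2, item 7, gives the visit four weeks later a different purpose, "to assess whether any change in symptoms and disease severity has occurred off therapy".

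Section 7 is the whole analysis plan. For GCSI it covers each treatment week and the four weeks after treatment: "Paired Student T-tests will be done comparing baseline with all other subsequent time points". Emptying at three times (before, end of treatment, four weeks later) is compared by ANOVA of unstated type. The three patient subgroups are also compared, at baseline and after treatment. No section ranks these tests, adjusts them or says what result counts as success.

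**The concern.** An error level belongs to a decision rule, and here the rule is missing. With two primary measures, a single 0.05 means one thing if both must succeed and another if either is enough. Section 7 widens the gap. It treats the end-of-treatment GCSI week no differently from the other weeks. It also folds the off-therapy visit into the emptying test, so a significant result would not by itself show that emptying changed between baseline and end of treatment.

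If this stays open, the success rule can be settled after the results are known, and a reader cannot tell whether a reported p-value carries the level stated in section 4.2. In an uncontrolled before-and-after study, prespecification is one of the few protections available.

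**Working it through.** **Inputs from the documents.** Two-sided alpha 0.05 (4.2); two primary measures (3.3, 4.2); N = 45, as three subgroups of 15 (4.2); three emptying times (section 7). The documents give no SD, correlation or dropout rate, so the correlations below are assumptions shown as ranges. The 0.05 is itself an input and cannot be reproduced without a rule. The sample size cannot be reproduced without an SD.

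**Step 1. Either measure suffices, one end-of-treatment contrast each at 0.05.**
- Independent: 1 − (1 − 0.05)² = 1 − 0.9025 = 0.0975.
- Ceiling under any dependence: 0.05 + 0.05 = 0.10.
- Test statistics correlated 0.3 / 0.5 / 0.7 (bivariate normal): 9.5% / 9.1% / 8.3%.

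A repeated-measures ANOVA in place of the paired emptying test also has a level of about 5%, so the same figures apply.

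**Step 2. Either suffices, but the emptying ANOVA ignores pairing.** Assume equal variance and a common within-patient correlation ρ across the three times. Under the null:
- between-time sum of squares ~ σ²(1 − ρ)χ² on 2 df;
- within-time sum of squares ~ σ²[(1 + 2ρ)χ² on 44 df + (1 − ρ)χ² on 88 df], referred to 132 df.

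The numerator shrinks by 1 − ρ and the denominator does not, so the test rejects too rarely. Overall error, if independent of GCSI, is 1 − 0.95 × (1 − ANOVA level):

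| ρ | ANOVA level (simulated) | Overall error |
|---|---|---|
| 0.3 | about 1.5% to 1.7% | 1 − 0.95 × 0.985 = 6.4%, to 1 − 0.95 × 0.983 = 6.6% |
| 0.5 | about 0.3% | 1 − 0.95 × 0.997 = 5.3% |
| 0.7 | about 0.01% | 1 − 0.95 × 0.9999 = 5.0% |

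At ρ = 0.3, a simulation of 4,000,000 replicates gave 1.5%; 1.7% is kept as the upper figure.

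**Step 3. Rules that hold 5%.**
- Both required, each at 0.05: if at least one null is true, success needs a false rejection of that null, so the error is at most 5% (0.05² = 0.25% if both nulls are true and the tests independent).
- Alpha shared at 0.025 each: at most 5% (1 − 0.975² = 4.94% if independent). Holm improves on this split at the same bound.
- Fixed sequence, each at 0.05: at most 5%.

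**Step 4. Cost at the 0.025 Holm step.** Detectable standardised paired change, noncentral t:

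| Population | 80% power: 0.05 → 0.025 | 90% power: 0.05 → 0.025 |
|---|---|---|
| Pooled, N = 45 | 0.43 → 0.47 | 0.49 → 0.54 |
| Subgroup, n = 15 | 0.78 → 0.88 | 0.90 → 1.00 |

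Both powers are shown because section 4.2 prints a Type II error of 0.10, which is 90% power, beside 80% power. Both populations are shown because the plan does not say whether the primary test is pooled.

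**The case against.** The strongest reply is that 0.05 appears under sample size as a design input for each comparison, and that no section promises study-wide control. On that reading each single paired test has its stated level. This limits the charge, since the plan does not break an explicit familywise promise. But the level is stated once, for a primary comparison that names both measures, and the plan still does not say how two results combine.

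Four stronger readings are tempting, and the documents do not support them.

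- *That the plan gives no indication of a primary time point.* Sections 4.2 and 5.2 and the assessment list together point to the 4-week assessment. What stands is that section 7 does not carry this through.
- *That the error simply is 9.75%.* That needs a 5%-level emptying test. Section 7 plans an ANOVA of unstated type, and Step 2 shows that the figure could be close to 5%. That is no defence of the plan, because it comes from an emptying test with almost no chance of rejecting.
- *That any significant GCSI week would count as success.* The error would then be larger: simulated at about 23% to 29% for eight weekly tests plus an independent emptying test, with assumed correlation 0.7 to 0.5 between weekly changes. The plan states no such rule, so this is not a property of the plan.
- *That 5% holds only if both measures are required.* A split or a fixed order holds it too.

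It can also be said that the word joining the two targets in 4.2 means both are required, or that listing emptying second in 3.3 sets an order. The first lists the effects to be detected and the second is a label; neither is written as a rule. Finally, 3.1 calls the study a pilot. That lowers the stakes but does not supply the rule.

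**Conclusion.** The concern holds in a limited form. The plan states 0.05 for two primary measures and omits the rule that would give the number a meaning. If either measure suffices and only the end-of-treatment GCSI test counts, the overall error is up to 9.75% with a 5%-level emptying test (independence assumed; 9.5% to 8.3% at correlation 0.3 to 0.7). It is about 6.6% to 5.0% if the ANOVA ignores pairing (assumed within-patient correlation 0.3 to 0.7). It is at most 5% if both are required, if alpha is shared, or under a fixed sequence. The documents do not choose among these. This should be fixed, but in a 45-patient single-arm pilot it bears on what the p-values mean and not on whether a change can be attributed to VNS.

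**What to change.** In section 7:

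1. Name baseline versus end of treatment (the 4-week assessment) as the single primary contrast for each measure, tested as a paired comparison in a stated population: all 45 pooled, or each subgroup of 15. If each subgroup is tested, the success rule must cover the three subgroups as well.
2. Make the three-time-point emptying ANOVA repeated-measures and supportive.
3. State one success rule: Holm at 0.05; or a fixed sequence of GCSI then emptying, the order in section 3.3; or both required, with no split.
4. Label all other weekly, post-treatment and subgroup tests secondary or descriptive, with 95% confidence intervals.
5. Reconcile the GCSI windows. Baseline is 1 week in Study Assessment and Monitoring, item 2 (counted from a randomization that this design does not have), and 2 weeks in the schedule of assessments. The post-treatment diary is 2 weeks in the schedule and 4 weeks in section 7. The two power figures in section 4.2 also need reconciling.

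The cost is wording; no visits or patients are added. Under Holm, the detectable change at 80% power rises from 0.43 to 0.47 standardised units if pooled, or from 0.78 to 0.88 at n = 15. A fixed sequence costs GCSI nothing, but emptying cannot be claimed if GCSI fails. Requiring both gives an overall power of 0.80 × 0.80 = 64% if each measure has 80%, or 0.90 × 0.90 = 81% if each has 90%, assuming independence.
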